- Subjects must have the ability to comply with basic instructions and be able to sit still comfortably with the sensor leads attached. Subjects previously diagnosed with a neurologic, cardiovascular, or psychophysiological disease such as ADHD, Asperger Syndrome, chronic pain, dyslexia, depression, insomnia, migraines, PTSD, substance abuse disorder, TBI, and others.
- During the screening process a list of questions, Appendix D, shall be asked to evaluate eligibility, severity and related concerns to be considered for treatment.

Exclusion Criteria:

- Subjects who fail to meet inclusion criteria.
- Subjects who are unable, unwilling, or incompetent to provide informed consent, assent and/or parental permission.
- Subjects physically unable to come to the study visits.
- Subjects with a known seizure disorder.
- Subjects with bilateral hearing impairment (treatment requires the use of headphones).
- Subjects receiving ongoing treatment with opiate, benzodiazepine, anti-psychotic or sleep medications, as well as some anti-depressants or stimulants, except those cases deemed acceptable by the investigator.
- Subjects with anticipated and ongoing use of recreational drugs except when deemed acceptable by the investigator.

Subjects are encouraged to discuss their participation with their healthcare provider following completion of HIRREM since some of their symptoms and conditions may be alleviated and therefore no longer require the same type or dosage of medication. Throughout the course of/ and for three weeks following treatment subjects will be requested to abstain from the consumption of alcohol or use of recreational drugs since the effects of these substances may cause reversal or cessation of the benefits of HIRREM. Additionally, subjects will be asked to discontinue chiropractic practices, cranial-sacral therapy, and bio-energy work during treatment and for the three weeks following treatment. Other instructions and requests may be given to the patient and will be contingent upon the condition(s) being treated and will be at the discretion of the investigator.

2) Number of Subjects:

This protocol is submitted with the intention of uncovering potential for future research and as such the aim is for three hundred subjects to be enrolled and receive HIRREM. This cohort will provide data across a variety of conditions, which can be used to generate estimates of effect size, and serve as pilot data in proposals for future studies.

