Follow-up visit will be scheduled for 4 -8 weeks after V2 treatment completion visit. Post intervention measures will be repeated.

4) High Resolution, Relational, Resonance-Based, Electroencephalic Mirroring (HIRREM)

HIRREM is an EEG-based, noninvasive technology to facilitate relaxation and auto-calibration of neural oscillations.

a. Brain Pattern Assessment

This is the first step in the process, occurring prior to the active HIRREM sessions. The assessment is to create a map of the frequencies and amplitudes in the brain. With the participant in a sitting or slightly reclined position, sensors are sequentially placed over seven areas of the scalp, and measurements are taken with eyes closed (1 minute), eyes partially open (1 minute), and eyes open (1 minute). For eyes closed, subjects are asked to rest and relax quietly. For eyes open, subjects are given standardized tasks such as numerical digit recall, reading silently, calculations, or listening comprehension. This allows

evaluation of the brain pattern with the brain at rest, and at task. The data are processed to identify patterns and imbalances, which will then be used to generate specific protocols for the HIRREM sessions that follow. The mapping takes up to 60 minutes to complete.

b. HIRREM Session

Each HIRREM session requires about 90-120 minutes.

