Baroreflex sensitivity (BRS) for control of HR, heart rate variability (HRV) and blood pressure variability (BPV): Continuous BP and HR are acquired from noninvasive finger arterial pressure measurements and ECG for a minimum of 8 minutes in subjects lying down quietly. SBP and RR intervals (RRI) files generated via the data acquisition system (BIOPAC acquisition system and software, Santa Barbara, CA) at 1000 Hz are analyzed using Nevrokard SA-BRS software (Nevrokard Kiauta, d.o.o., Izola, Slovenia) for measures of BRS, HRV and BPV as follows: Frequency Method. Power spectral densities of SBP and RRI oscillations are computed by 512 points Fast Fourier Transform (FFT) and integrated over specified frequency ranges (LF: 0.04-0.15 Hz; HF: 0.15-0.4 Hz). A Hanning window is applied and the their squared-coherence modulus is computed if coherence is >0.5 as reported (16). The square-root of the ratio of RRI's and SBP powers is computed to calculate LF, HF alpha indices, which reflect BRS (16). Power of RRI spectra in LF, HF range (LF_{RRI} and HF_{RRI}) are calculated in normalized units and the ratio of LF_{RRI}/HF_{RRI} is used as a measure of sympathovagal balance (17). Power of SBP spectra calculated as LF_{SAP} is used as a measure of BPV. Sequence Method. BRS calculated by this method is based on quantification of sequences of at least three beats (n) in which SBP consecutively increases (UP sequence) or decreases (DOWN sequence), which are accompanied by changes in the same direction of the RRI of subsequent beats (n+1). The software scans the RRI and SBP records, identifies sequences, and calculates linear correlation between RRI and SBP for each sequence. If the correlation coefficient exceeds a pre-set critical value (0.85), the regression coefficient (slope) is calculated and accepted. The mean of all individual regression coefficients (slopes), a measure of sequence BRS, is then calculated for Sequence UP, DOWN and TOTAL. Time-Domain Analysis. Three time-domain parameters are used for hemodynamic variability (18, 19). HRV is determined by computing the standard deviation of beat-to-beat interval (SDRR) and the root mean square of successive beat-to-beat differences in R-R interval duration (rMSSD). BPV is the standard deviation of the mean arterial pressure (SDMAP).

ii. HRV Data Processing and Interpretation

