Reaction time testing will be measured by the clinical reaction time apparatus. It is constructed from a meter stick covered in the friction tape with gradations. The modified meter stick is fixed to a weighted rubber cylinder. The apparatus is placed between the thumb and index finger of the subject and released at a random time during a countdown. The subject catches the apparatus and the distance fallen is converted to reaction. This simple clinical measure has been evaluated by Eckner et al and demonstrated utility in testing comparable to computerized testing methods.³³

g. T3/T4 Asymmetry

The proprietors of HIRREM have repeatedly observed that EEG asymmetries in the temporal lobes (specifically at T3 and T4 in the 10-20 International System for EEG correspond to autonomic dysfunction. When T4 signals are dominant to T3 signals a sympathetic state is favored which is manifested as symptoms of anxiety, cardiovascular over-drive, and

hyperarousal. When T3 signals are excessively dominant to T4 signals a parasympathetic state is favored which is manifested as symptoms of emotional numbness, cardiovascular underactivity, GI dysfunction, and under-arousal. Lateralization of autonomic activity is not a novel finding, it is in accord with a number of previously published studies which support a hypothesis of autonomic lateralization posited by Craig and previously discussed.^{16,28-32} Utilization of HIRREM at T3 and T4 has demonstrated success in ameliorating symptoms associated with autonomic disruption. EEG balance at T3 and T4 is indicative of autonomic balance and benefit according to BST.

Our preliminary data demonstrate correlation between a T3/T4 temporal asymmetry score and objective physiological changes reflective of autonomic signaling to the heart at the baseline assessment. Comparison of such activity at T3 and T4 over time will provide objective physiological outcome data regarding the effect of HIRREM on autonomic balance and function.

6) Statistical Analysis

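### Does leaving the baseline T3/T4 score out of the HRV models hide a response that differs by side?

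*Combined protocol and SAP*

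**What the plan says.** Section 5(g), T3/T4 Asymmetry, states two directions: "When T4 signals are dominant to T3 signals a sympathetic state is favored", and "When T3 signals are excessively dominant to T4 signals a parasympathetic state is favored". It then gives the desired end state: "EEG balance at T3 and T4 is indicative of autonomic balance and benefit according to BST". It also gives the score a role in the study: "Comparison of such activity at T3 and T4 over time will provide objective physiological outcome data".

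The background reports that, in 23 consecutive subjects of this same project, pre-treatment T3/T4 asymmetry correlated significantly with RMS-SD. No coefficient is given. The Objectives anticipate one overall direction, an increase in HRV parameters. Section 5(a)(i) computes several of them, among them the LF/HF ratio, which "is used as a measure of sympathovagal balance".

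Section 6 names three analyses:
- a primary comparison of disorder groups on post-treatment HRV, adjusted for the baseline value;
- repeated-measures models for the secondary measures;
- an exploratory look at common effects in consecutively enrolled subjects.

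Tests are two-tailed at 0.05. Section 2 sets a target of 300 subjects, to supply data "which can be used to generate estimates of effect size, and serve as pilot data in proposals for future studies".

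**The concern.** If T4-dominant subjects start in sympathetic excess and T3-dominant subjects in parasympathetic excess, a move toward balance might raise an HRV measure in one set and lower it in the other. The idea is most direct for LF/HF. Averages over both sides would then shrink, and two disorders could differ only because they contain different shares of T3- and T4-dominant subjects.

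The study exists to hand effect sizes and hypotheses to later trials, so a diluted or misattributed effect would be passed on. The protocol itself ties the score to cardiac autonomic measures, and using it would need no new data. That makes its absence from the HRV models look like an oversight.

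**Working it through.** **1. The text.** A side-dependent HRV response is an inference. The protocol gives T3-dominant subjects a parasympathetic state but no direction of HRV change. The introduction links many, if not all, of the target conditions with low HRV or other abnormal measures, which leaves a general rise possible. The two directions are not mirror images either: T4 need only be dominant, whereas T3 must be excessively so. The correlation in 23 subjects is between two baseline measures and says nothing about response to treatment.

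**2. Pooled before-after change.** There is no planned figure to reproduce, since the protocol gives no effect, SD, mix of sides or disorder-group size. From the protocol: n = 300, two-sided 0.05. Assumed: correlation ρ = 0.7 between visits, change +0.3 SD in T4-dominant subjects, d in T3-dominant subjects, a share w T4-dominant, every subject on one side, all 300 evaluable.

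Mean = 0.3w + d(1 − w). SD = √[2(1 − ρ) + w(1 − w)(0.3 − d)²]. Power is from the non-central t distribution.

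Example, w = 0.6 and d = −0.3: mean = 0.18 − 0.12 = 0.06; SD = √(0.6 + 0.24 × 0.36) = 0.828; power 24%.

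| Mix T4/T3 | d = −0.3 | d = −0.15 | d = 0 |
|---|---|---|---|
| 80/20 | 0.18 SD, 97% | 0.21 SD, 99.5% | 0.24 SD, >99.9% |
| 70/30 | 0.12 SD, 71% | 0.165 SD, 95% | 0.21 SD, 99.6% |
| 60/40 | 0.06 SD, 24% | 0.12 SD, 73% | 0.18 SD, 98% |
| 50/50 | 0 SD, 5% | 0.075 SD, 36% | 0.15 SD, 91% |

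The loss is severe only for opposite effects near an even mix. If both sides rise equally there is none. This is also the exploratory pooled analysis, not the primary one.

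**3. Primary disorder comparison.** The gap between two disorders from mix alone is (w_A − w_B)(0.3 − d).
- 80% against 40% T4-dominant: 0.4 × 0.6 = 0.24 SD at d = −0.3, 0.18 at −0.15, 0.12 at 0.
- 60% against 50%: 0.06, 0.045 and 0.03 SD.

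With an assumed 50 subjects per disorder, the variance after baseline adjustment is 1 − 0.7² = 0.51, plus w(1 − w)(0.3 − d)². In the largest case: SE = √[(0.568 + 0.596)/50] = 0.153, 95% CI half-width 0.30 SD, power about 34%. Over the six cases the half-width is 0.29 to 0.31 SD, so every gap is smaller than the uncertainty around it.

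**4. What a score term would show.** Suppose there is no side difference, n = 300, ρ = 0.7 and a score-baseline HRV correlation of 0.3. Two descriptions of HRV are plausible.
- *Each subject has a stable level plus noise.* The score slope in the baseline-adjusted model is (0.3 − 0.7 × 0.3)/(1 − 0.3²) = 0.099, although nothing differs by side. Residual variance is 1 − (0.49 + 0.09 − 0.126)/0.91 = 0.501; SE = √[0.501/(300 × 0.91)] = 0.043; ratio 2.31; rejection about 64%. Simulation gives 62% to 64%. Regressing change on score rejects about 5%.
- *All subjects regress to a common mean.* The baseline-adjusted model rejects at about the nominal 5%, but the slope of change on score is (0.7 − 1) × 0.3 = −0.09; SE = √[(0.6 − 0.0081)/300] = 0.044; ratio 2.03; rejection about 53%. Simulation gives about 52%.

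Each model is valid under one description and misleading under the other. Without a control arm, the data at hand cannot separate either from a treatment effect. The bias arises exactly when score and baseline HRV correlate, which is what the protocol reports.

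**The case for a change.** The strongest case for acting is that the protocol singles out this marker. It ties the score to cardiac autonomic measures and wants to identify cohorts that are not obvious in advance. A T3/T4-defined cohort is a natural candidate, and grouping by disorder alone does not reveal it. An unplanned look later would leave many choices open: the score's formula and sign, which of three eye conditions to use, and which of many HRV parameters.

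Much of this is true as description. No planned model has a T3/T4 term, and the score's formula and balance point are not given. Larger groups would also bring the largest mix gap into view: with 150 per disorder, SE = √(1.164/150) = 0.088, the ratio is 0.24/0.088 = 2.72 and power is about 78%.

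It still does not make a defect. A disorder average over the mix of sides recruited remains a correct estimate of the average response in that disorder, which is what section 6 sets out to estimate. The response by side is not lost: the score is a listed item, the assessment precedes the sessions, the team has already related it to HRV, and section 6 does not close the list of exploratory analyses. The accurate description is that this analysis is not pre-specified, and the same could be said of age, medication or number of sessions. The missing score definition is a matter of detail. No signed T3/T4 analysis is planned in which shifts toward balance would cancel, and section 5(g) already names balance as the benefit.

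**Conclusion.** The concern does not hold. The plan contains no contradiction, and no stated rule or figure gives a wrong result. A response that differs by side is a hypothesis the protocol does not state. Its cost to the pooled estimate runs from nothing (equal effects) to complete cancellation (opposite equal effects at 50/50), entirely according to assumed values.

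The obvious addition would not tell these cases apart, given false rejection of about 62% or 52% under the two descriptions of HRV. Those rates rest on the assumed correlation of 0.3, n = 300 and ρ = 0.7. Showing both models without a control arm or a decision rule leaves the question open and could itself seed a spurious hypothesis.

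In an uncontrolled, hypothesis-generating study, whether to examine one more moderator is the investigators' choice. No change is needed.

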- The primary objective of this proposal is to generate new hypotheses and data for future studies by evaluating the effect of HIRREM as supplemental care for subjects with a number of neurological, cardiovascular, and psychophysiological diseases. The primary analytic outcome to determine the effect and feasibility of HIRREM is HRV as measured by standard outcomes collected using a BIOPAC device for continuous recording of heart rate and blood pressure. This also allows calculation of mean arterial pressure and baroreceptor sensitivity. We anticipate a decrease in sympathetic activity and an improvement in sympatho-vagal balance manifested as an increase in HRV parameters.
- Secondary objectives of this proposal include evaluation of the effects of HIRREM on:
 - Autonomic nervous system functions, as manifested by blood pressure and heart rate. Another expected result of a decrease in sympathetic activity and an improvement of sympatho-vagal balance may be a decrease in heart rate and blood pressure.
 - Psycho-physiological functional outcomes as measured using a standardized measure of health status the (EQ-5D), the Center for Epidemiologic Studies Depression Scale (CES-D), the GAD-7 measure of anxiety, the Insomnia Severity Index (ISI), and the PTSD Check List for civilians or military service members (PCL-C, or PCL-M, respectively). We expect to see an improvement in these measures following HIRREM.
 - Metrics for specific disorders will be measured according to relevant currently accepted assessment tools. Some of the conditions for which treatment is anticipated and the corresponding evaluation tools are in Appendix A. We expect to see improvement in these measures.

- Weight will be measured at the enrollment visit (V1), completion visit (V2) and follow-up visit (V3) to determine the potential impact of HIRREM on weight.
- Reaction time will be measured using the clinical reaction time enrollment visit (V1), completion visit (V2) and follow-up visit (V3).

Research Design and Methods:

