This protocol is an assessment of the functional and physiological effects of HIRREM on neurological, cardiovascular, and neurophysiological disorders. It will be a non-randomized, open label, and unblinded before-and-after trial. The intention of this protocol is to evaluate the effect of HIRREM on an objective, physiological common denominator (HRV), across a variety of relevant conditions, as well as changes in clinical symptoms scales, to generate hypotheses and pilot data for investigation in future proposals. HIRREM will be offered as deemed potentially advantageous by the investigator. Patients will be recruited to receive eight to twenty HIRREM sessions in addition to their usual care. HIRREM sessions will be completed over a one month period. Measurements for the primary and secondary outcomes will be obtained at the initial visit and after completion of HIRREM therapy. A follow-up visit (V3) will be performed four to eight weeks after the completion visit (V2). This will consist of several representative questionnaires and surveys and a repeat of recording of blood pressure and heart rate using the BIOPAC device.

1) Subjects Selection Criteria:

Male and Female adults and children over the age of 11 years with a clinical diagnosis consistent with the aims of this proposal, who also meet the inclusion criteria outlined below and are interested in receiving HIRREM, will be enrolled. Subjects will be recruited by physician referral, word of mouth, and through advertisement. Physicians who want to inform prospective subjects about the availability of the research will be provided with copies of the IRB approved consent form and IRB approved ad which they may give to prospective subjects. The physicians do not obtain subjects' consent for the research or act as representatives of the investigators. Physicians provide prospective subjects with information about contacting investigators for information or enrollment; and/or seek or obtain the prospective subjects' permission for investigators to contact them. The participant must be able to provide informed consent.

Inclusion Criteria:

- Male and female adults and children aged 11 years and older.
- Subjects who are over the age of 18 must be able to give informed consent. Children must be able to sign an assent form and have a signed parental permission form.

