Data will be analyzed using the most recent versions of SAS (SAS Institute, Inc., Cary, NC). Prior to performing analyses related to the hypotheses, histograms and descriptive statistics will be computed to examine the characteristics and distributions of the data. As detailed below, analytical methods will be conducted through generalized linear models that allow specification of appropriate distribution as well as various covariance types to ensure that inference tests can be interpreted conventionally. If required, nonparametric equivalents to the proposed methods will be used to analyze variables not well characterized by standard distributions. Unless otherwise stated, all relevant analyses will be two-tailed and $p < 0.05$ will be used to determine statistical significance. Because this proposal is designed to estimate effect sizes for future pilot and definitive trials, care will be taken to provide point estimates of effect size for each outcome along with corresponding 95% CI.

This primary objective of this protocol is to evaluate the effect of HIRREM in neurological, cardiovascular, and psychophysiological disorders as measured by standard HRV parameters. Also, a variety of secondary outcomes will assess the impact on functional and physiological measures (BP and HR), a number of standard disorder specific clinical measures, and subjective psychophysiological outcomes. The primary analysis will be examining group differences on the post-HIRREM measure while controlling for baseline levels (i.e., group treated as a fixed effect, with baseline scores entered as a covariate in a generalized model assuming a normal distribution and identity link). Changes in all secondary measures will be indexed using the GLM using the repeated measurements within each individual. The groups will be comprised of a collection of individuals from within the study with a common clinical disorder, although exploratory analysis will also evaluate for common effects in consecutively enrolled subjects.

Human Subjects Protection:

1) Consent and Assent

Written informed consent, or assent and parental permission will be obtained by the research staff from each competent subject.

2) Confidentiality and Privacy

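### The primary HRV analysis compares treated disorder groups with each other, so it cannot test whether HRV rises after HIRREM; the within-subject change should be named as primary

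*Combined protocol and SAP*

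**What the plan says.** Under Objectives and Hypotheses, HRV is the primary outcome and a direction is given: "We anticipate a decrease in sympathetic activity and an improvement in sympatho-vagal balance manifested as an increase in HRV parameters". Research Design and Methods describes the design: "It will be a non-randomized, open label, and unblinded before-and-after trial". It gives the measurement times as follows: "Measurements for the primary and secondary outcomes will be obtained at the initial visit and after completion of HIRREM therapy". It also presents HRV as a physiological measure shared across conditions. Under Number of Subjects, the aim is 300 people, all of whom are to receive HIRREM. No untreated or sham group is described.

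Section 6 restates the primary objective as the effect of HIRREM on standard HRV parameters and then fixes the analysis: "The primary analysis will be examining group differences on the post-HIRREM measure while controlling for baseline levels". Group is a fixed effect, baseline is a covariate, and the model is normal with an identity link. The grouping is defined: "The groups will be comprised of a collection of individuals from within the study with a common clinical disorder".

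Three other statements in section 6 bear on change:
- For secondary outcomes: "Changes in all secondary measures will be indexed using the GLM using the repeated measurements within each individual".
- For all subjects together: "exploratory analysis will also evaluate for common effects in consecutively enrolled subjects".
- For estimation: "care will be taken to provide point estimates of effect size for each outcome along with corresponding 95% CI".

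**The concern.** The objective asks whether HRV goes up from before HIRREM to after it. The primary model asks whether, at equal baseline, one treated disorder ends higher than another. Every group is treated, so no group contrast in that model is a contrast with no treatment or with the subject's own earlier state. A rise common to all disorders goes into the intercept, which the plan does not test.

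The study exists to supply effect sizes for later trials. If HRV rose by a similar amount in every disorder, the primary result would be null even though the expected change had occurred. The effect size and CI are promised without saying of what, so two analysts could report different HRV effects from the same data: a disorder difference, an adjusted post-treatment mean, or a change.

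**Working it through.** **Inputs from the documents.** Target 300 subjects, all treated; two-sided 0.05; ANCOVA of the post value on baseline and disorder. The documents give no power calculation, HRV standard deviation, correlation between visits, dropout or group sizes, so there is no planning figure to reproduce. Correlations, group layouts, rises and the 240-subject case below are assumptions.

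**1. The group test does not respond to a shared rise.** The model is post = a_g + b × baseline + error, and the test is of equal a_g. Adding a constant c to every post value replaces each a_g by a_g + c. Differences between groups, the slope b and both residual sums of squares stay the same, so F stays the same. Multiplying every post value by a constant scales both sums of squares equally and also leaves F unchanged. No assumed input is needed.

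Numerical check on one simulated data set (300 subjects, six groups):

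| Change to every post value | Group F (p) | Paired t |
|---|---|---|
| none | 0.388 (0.857) | 0.10 |
| +5 units | 0.388 (0.857) | 6.88 |
| +10 units | 0.388 (0.857) | 13.67 |
| ×1.2 | 0.388 (0.857) | 9.64 |

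**2. Size under assumptions.** For a shared rise d (in SD units) and correlation r, the SD of the change is √(2(1−r)). The paired test has noncentrality d√n / √(2(1−r)) on n−1 degrees of freedom. With d = 0.2 and complete data:

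| n | r | Noncentrality | Paired power | Planned group test |
|---|---|---|---|---|
| 300 | 0.6 | 0.2×17.32/0.894 = 3.87 | 97% | about 5% |
| 300 | 0.9 | 0.2×17.32/0.447 = 7.75 | 100% | about 5% |
| 300 | 0.5 | 0.2×17.32/1 = 3.46 | 93% | about 5% |
| 240 | 0.5 | 0.2×15.49/1 = 3.10 | 87% | about 5% |

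By step 1, the group test's rejection rate under a shared rise is its rate under no rise, which is 5% when disorders do not otherwise differ.

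**3. Precision of the change.** The 95% CI half-width is t(0.975, n−1) × √(2(1−r)/n). For n = 300 it is 0.10 SD at r = 0.6 and 0.05 SD at r = 0.9. For a disorder with n = 30 it is 0.33 SD and 0.17 SD.

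**4. Extracting a change from the planned model needs a further choice.** The adjusted post mean of disorder g at baseline x0, minus x0, equals the disorder's observed mean change + (1−b)(its baseline mean − x0). Weighting by group size gives the pooled figure: overall mean change + (1−b)(overall baseline mean − x0). The pooled figure therefore equals the mean change at x0 = the overall baseline mean, and at no other x0 unless b = 1.

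Take b = 0.6 and an observed change of 0.20 SD in every disorder:
- Pooled, x0 set 0.5 SD below the overall mean: 0.20 + 0.4×0.5 = 0.40.
- Pooled, x0 set 0.5 SD above it: 0.20 − 0.4×0.5 = 0.00.
- By disorder, at the overall mean, for baselines 0.3 SD above and 0.3 SD below it: 0.20 + 0.12 = 0.32 and 0.20 − 0.12 = 0.08.

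Section 6 states neither x0 nor the weights.

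**5. What the planned test does detect.** Suppose five of ten disorders of 30 rise by 0.4 SD and five do not, with r = 0.7. Group effects are ±0.2 around their mean and the residual variance is 1 − 0.49 = 0.51, so the noncentrality is 300×0.04/0.51 = 23.5 on 9 and 289 degrees of freedom. Power is 94%.

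**The case against.** The strongest defence is that the plan already covers much of this. It looks for effects common to consecutively enrolled subjects, promises an estimate and CI for every outcome (HRV included), and calls itself before-and-after. The study generates hypotheses and no decision hangs on the primary p-value, so the label primary or exploratory matters less than in a confirmatory trial. The background also names a goal that the between-disorder comparison serves well, namely finding cohorts worth further study; step 5 shows that it can do so.

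Much of that stands. A reader might infer that the plan never looks at HRV change, or that the planned model is useless. The documents support neither. What remains is that the analysis carrying the word primary does not address the primary hypothesis, the one that would do so is exploratory with no model given, and the contrast behind the promised HRV effect size is unnamed. If each disorder were instead meant to be analysed alone, group would have one level and the stated fixed effect would have nothing to compare.

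Two further points are fair. The power figures depend on assumed correlations and complete data. And naming the change does not settle everything: the HRV processing section lists 13 statistics without choosing one, and the medical history form allows several conditions per subject, so membership of a disorder group needs a rule.

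**Conclusion.** The concern holds. The stated primary test cannot detect an HRV rise shared by all subjects, whatever its size, and that part rests on algebra alone. The contrast of about 5% rejection against 97% to 100% for a 0.2 SD rise rests on 300 complete subjects and a correlation of 0.6 to 0.9. With correlation 0.5 the paired figure is 93%, or 87% at 240 subjects. Because the study is exploratory, this should be fixed but does not undermine the data.

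Two stronger readings should be resisted. First, a significant paired test would not show that HIRREM raised HRV: it would respond to a shift of that size from any cause. Usual care continues throughout. The requested abstinence from alcohol and recreational drugs, and the stopping of certain other therapies, run until three weeks after treatment, while V2 falls within two weeks of it. Regression to the mean in HRV is possible, but the entry criteria set no HRV threshold, so it is not shown. Second, replacing ANCOVA by a comparison of change scores between disorders would not be safer in itself. In non-randomised groups the two can disagree, and which one misleads depends on whether disorder means are stable or converge between visits. The documents do not say.

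**What to change.** Rewrite the primary-analysis paragraph of section 6:
- Name the within-subject V1-to-V2 change in HRV, with 95% CI, overall and by disorder, as the primary analysis. The repeated-measures approach already assigned to secondary measures can be used, with its visits and covariance structure stated.
- Name the HRV statistic to which this applies, and how subjects with several conditions enter the by-disorder estimates.
- Keep the baseline-adjusted comparison between disorders as a secondary heterogeneity analysis serving the cohort-identification goal. State the baseline value and weights for any adjusted mean, and note that ANCOVA and change-score comparisons of non-randomised groups can disagree.
- State that without a control arm the change cannot be attributed to HIRREM alone, because usual care, the requested abstinence and stopping of other therapies, and possible regression to the mean cover the same interval.

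The cost is one rewritten paragraph and a dated amendment; the date matters because the background reports that subsets of these subjects have already been analysed. HRV is already measured at both visits, so no new data or visits are needed.
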